10.6. Source Documents

Source documents provide evidence for the existence of the participant and substantiate the integrity of the data collected. Source documents are filed at the Investigator's site.

Data reported on the CRF or entered in the eCRF that are transcribed from source documents must be consistent with the source documents or the discrepancies must be explained. The Investigator may need to request previous medical records or transfer records, depending on the clinical trial.

The required source data should include sequential notes containing at least the following information for each participant:

- participant identification (name, date of birth, sex)
- documentation that participant meets eligibility criteria, ie, history, physical examination, and confirmation of diagnosis (to support inclusion and exclusion criteria)
- participation in trial (including trial number)
- trial discussed and date of informed consent
- dates of all visits
- documentation that protocol-specific procedures were performed
- results of efficacy parameters, as required by the protocol
- start and end date (including dose regimen) of trial medication (preferably drug dispensing and return should be documented as well)
- record of all AEs and other safety parameters (start and end date, and preferably including causality and intensity)
- concomitant medication (including start and end date, dose if relevant; dose changes should be motivated)
- date of trial completion and reason for early discontinuation, if applicable

10.7. Clinical Trial Files and Retention of Records

The Investigator must maintain adequate and accurate records to enable the conduct of the clinical trial to be fully documented and the clinical trial data to be subsequently verified. These documents should be classified into at least the following 2 categories: (1) Investigator's clinical trial file, and (2) participant clinical source documents.

The Investigator's clinical trial file will contain the protocol/amendments, CRF and query forms, IRB and governmental approval with correspondence, informed consent, drug records, staff curriculum vitae and authorization forms, and other appropriate documents and correspondence.

All clinical trial documents must be retained by the Investigator until at least 2 years after the last approval of a marketing application in an ICH region (ie, United States, Europe, or Japan) and until there are no pending or contemplated marketing applications in an ICH region; or, if no application is filed or if the application is not approved for such indication, until 2 years after the investigation is discontinued and regulatory authorities have been notified. Investigators may be

required to retain documents longer if required by applicable regulatory requirements, by local regulations, or by an agreement with the Sponsor. The Investigator must notify the Sponsor before destroying any clinical trial records.

Should the Investigator wish to assign the clinical trial records to another party or move them to another location, the Sponsor must be notified in advance. If the Investigator cannot guarantee this archiving requirement at the clinical trial site for any or all of the documents, special arrangements must be made between the Investigator and the Sponsor to store these in sealed containers outside of the site so that they can be returned sealed to the Investigator in case of a regulatory audit.

10.8. Clinical Trial and Site Closure

The Sponsor reserves the right to close the clinical trial site or terminate the clinical trial at any time for any reason at the sole discretion of the Sponsor. Clinical trial sites will be closed upon clinical trial completion. A clinical trial site is considered closed when all required documents and clinical trial supplies have been collected and a clinical trial site closure visit has been performed.

The Investigator may initiate clinical trial site closure at any time, provided there is reasonable cause and sufficient notice is given in advance of the intended termination.

Reasons for the early closure of a clinical trial site by the Sponsor or Investigator may include but are not limited to:

- Failure of the Investigator to comply with the protocol, the requirements of the IRB/IEC or local health authorities, the Sponsor's procedures, or GCP guidelines
- Inadequate recruitment of participants by the Investigator
- Discontinuation of further study drug development

10.9. Clinical Study Report

A CSR will be prepared and provided to the regulatory agency(ies). The Sponsor will ensure that the report meets the standards set out in the ICH Guideline for Structure and Content of Clinical Study Reports (ICH E3). An abbreviated report may be prepared as applicable.

10.10. Publication Policy

The results of this clinical trial may be published or presented at scientific meetings. If this is foreseen, the Investigator agrees to submit all manuscripts or abstracts to the Sponsor before submission. This allows the Sponsor to protect proprietary information and to provide comments.

The Sponsor will comply with the requirements for publication of clinical trial results. In accordance with standard editorial and ethical practice, the Sponsor will generally support publication of multi-center studies only in their entirety and not as individual site data. In this case, a coordinating Investigator will be designated by mutual agreement.

Authorship will be determined by mutual agreement and in line with International Committee of Medical Journal Editors authorship requirements.

12. APPENDICES

APPENDIX 1. CLINICAL LABORATORY EVALUATIONS

The tests detailed in Appendix Table 1 will be performed by a central laboratory.

Protocol-specific requirements for inclusion or exclusion of participants are detailed in [Section 5](#) of the protocol.

Additional tests may be performed at any time during the clinical trial as determined necessary by the Investigator or required by local regulations.

Appendix Table 1: Protocol-Required Laboratory Assessments

Clinical Chemistry	Hematology	Urinalysis
Alanine aminotransferase (ALT) Alkaline phosphatase Aspartate aminotransferase (AST) Bicarbonate Blood urea nitrogen (BUN) Calcium Chloride Creatinine Glucose Potassium Sodium Total and direct bilirubin Total protein	Hematocrit Hemoglobin Mean corpuscular hemoglobin Mean corpuscular hemoglobin concentration Mean corpuscular volume Platelet count Red blood cell (RBC) count RBC distribution width White blood cell (WBC) count WBC differential (absolute): 
 ○ Basophils ○ Eosinophils ○ Lymphocytes ○ Monocytes ○ Neutrophils 	Bilirubin Glucose Ketones Leukocyte esterase Nitrite Blood pH Specific gravity Protein Urobilinogen Microscopic exam including bacteria, casts, crystals, epithelial cells, RBCs, and WBCs (if protein, leukocyte esterase, nitrite, or blood is positive)
Drug Screen	Coagulation Factors (Screening only)	Other Tests
Including but not limited to: Amphetamines Barbiturates Benzodiazepines (Stable use of ≤ 2 mg of lorazepam/day is allowed) Cannabinoids (THC) Cocaine (metabolite) Methadone Opiates Phencyclidine	Activated partial thromboplastin time Prothrombin time and international normalized ratio	Serum and urine pregnancy, (women of childbearing potential only) Viral Serology Screen (at Screening only): Hepatitis B surface antigen (HBsAg) and Hepatitis C virus (HCV) antibody and HIV antibody/antigen Urinary albumin Urinary creatinine (Part A only) 

APPENDIX 2. ADVERSE EVENTS: DEFINITIONS AND PROCEDURES FOR RECORDING, EVALUATING, FOLLOW-UP, AND REPORTING

Definition of Adverse Events

AE Definition

 • An AE is any untoward medical occurrence in a patient or clinical trial participant, temporally associated with the use of study drug, whether or not considered related to the study drug. • NOTE: An AE can therefore be any unfavorable and unintended sign (including an abnormal laboratory finding), symptom, or disease (new or exacerbated) temporally associated with the use of study drug.
Events Meeting the AE Definition

 • Any abnormal laboratory test results (hematology, clinical chemistry, or urinalysis) or other safety assessments (eg, ECG, radiological scans, vital signs measurements), including those that worsen from baseline, considered clinically significant in the medical and scientific judgement of the Investigator (ie, not related to progression of underlying disease). • Exacerbation of a chronic or intermittent pre-existing condition including either an increase in frequency and/or intensity of the condition. • New conditions detected or diagnosed after study drug administration even though it may have been present before the start of the clinical trial. • Signs, symptoms, or the clinical sequelae of a suspected drug-drug interaction. • Signs, symptoms, or the clinical sequelae of a suspected overdose of either study drug or a concomitant medication. Overdose per se will not be reported as an AE/SAE unless it is an intentional overdose taken with possible suicidal/self-harming intent. Such overdoses should be reported regardless of sequelae. • For efficacy studies: “Lack of efficacy” or “failure of expected pharmacological action” per se will not be reported as an AE or SAE. Such instances will be captured in the efficacy assessments. However, the signs, symptoms, and/or clinical sequelae resulting from lack of efficacy will be reported as AE or SAE if they fulfil the definition of an AE or SAE.
Events NOT Meeting the AE Definition

 • Any clinically significant abnormal laboratory findings or other abnormal safety assessments which are associated with the underlying disease, unless judged by the Investigator to be more severe than expected for the participant’s condition. • The disease/disorder being studied or expected progression, signs, or symptoms of the disease/disorder being studied, unless more severe than expected for the participant’s condition. • Medical or surgical procedure (eg, endoscopy, appendectomy): the condition that leads to the procedure is the AE. • Situations in which an untoward medical occurrence did not occur (social and/or convenience admission to a hospital). • Anticipated day-to-day fluctuations of pre-existing disease(s) or condition(s) present or detected at the start of the clinical trial that do not worsen.

Definition of SAE

If an event is not an AE per definition above, then it cannot be an SAE even if serious conditions are met (eg, hospitalization for signs/symptoms of the disease under study, death due to progression of disease).

An SAE is defined as any untoward medical occurrence that, at any dose:
a. Results in death
b. Is life-threatening

 The term 'life-threatening' in the definition of 'serious' refers to an event in which the participant was at risk of death at the time of the event. It does not refer to an event, which hypothetically might have caused death, if it were more severe.
c. Requires inpatient hospitalization or prolongation of existing hospitalization

 In general, hospitalization signifies that the participant has been detained (usually involving at least an overnight stay) at the hospital or emergency ward for observation and/or treatment that would not have been appropriate in the physician's office or outpatient setting. Complications that occur during hospitalization are AEs. If a complication prolongs hospitalization or fulfills any other serious criteria, the event is serious. When in doubt as to whether "hospitalization" occurred or was necessary, the AE should be considered serious. Hospitalization for elective treatment of a pre-existing condition that did not worsen from baseline is not considered an AE.
d. Results in persistent disability/incapacity

 The term disability means a substantial disruption of a person's ability to conduct normal life functions. This definition is not intended to include experiences of relatively minor medical significance such as uncomplicated headache, nausea, vomiting, diarrhea, influenza, and accidental trauma (eg, sprained ankle) which may interfere with or prevent everyday life functions but do not constitute a substantial disruption.
e. Is a congenital anomaly/birth defect
f. Important Medical Event:

 Medical or scientific judgement should be exercised in deciding whether SAE reporting is appropriate in other situations such as important medical events that may not be immediately life-threatening or result in death or hospitalization but may jeopardize the participant or may require medical or surgical intervention to prevent one of the other outcomes listed in the above definition. These events should usually be considered serious. Examples of such events include invasive or malignant cancers, intensive treatment in an emergency room or at home for allergic bronchospasm, blood dyscrasias or convulsions that do not result in hospitalization, or development of drug dependency or drug abuse.

Recording and Follow-Up of AE and/or SAE**AE and SAE Recording**

- When an AE/SAE occurs, it is the responsibility of the Investigator to review all documentation (eg, hospital progress notes, laboratory reports, and diagnostics reports) related to the event.
- The Investigator will then record all relevant AE/SAE information in the CRF.
- It is **not** acceptable for the Investigator to send photocopies of the participant's medical records in lieu of completion of the AE/SAE CRF page.
- There may be instances when copies of medical records for certain cases are requested. In this case, all participant identifiers, with the exception of the participant number, will be redacted on the copies of the medical records before submission.
- The Investigator will attempt to establish a diagnosis of the event based on signs, symptoms, and/or other clinical information. Whenever possible, the diagnosis (not the individual signs/symptoms) will be documented as the AE/SAE.

Assessment of Intensity

The Investigator will make an assessment of intensity for each AE and SAE reported during the clinical trial and assign it to one of the following categories:

- Mild: An event that is easily tolerated by the participant, causing minimal discomfort and not interfering with everyday activities.
- Moderate: An event that causes sufficient discomfort and interferes with normal everyday activities.
- Severe: An event that prevents normal everyday activities. An AE that is assessed as severe should not be confused with an SAE. Severe is a category utilized for rating the intensity of an event; and both AEs and SAEs can be assessed as severe.

An event is defined as 'serious' when it meets at least 1 of the predefined outcomes as described in the definition of an SAE, NOT when it is rated as severe.

Assessment of Causality

- The Investigator is obligated to assess the relationship between study drug and each occurrence of each AE/SAE.
- A "reasonable possibility" of a relationship conveys that there are facts, evidence, and/or arguments to suggest a causal relationship, rather than a relationship cannot be ruled out.
- The Investigator will use clinical judgement to determine the relationship.
- Alternative causes, such as underlying disease(s), concomitant therapy, and other risk factors, as well as the temporal relationship of the event to study drug administration will be considered and investigated.
- The Investigator will also consult the [Investigator's Brochure \(IB\)](#) and/or Product Information, for marketed products, in his/her assessment.
- For each AE/SAE, the Investigator **must** document in the medical notes that he/she has reviewed the AE/SAE and has provided an assessment of causality.
- There may be situations in which an SAE has occurred and the Investigator has minimal information to include in the initial report. However, **it is very important that the Investigator always make an assessment of causality for every event before the initial transmission of the SAE data.**
- The Investigator may change his/her opinion of causality in light of follow-up information and send an SAE follow-up report with the updated causality assessment.

- The causality assessment is one of the criteria used when determining regulatory reporting requirements.
- A medically qualified Investigator must assess the relationship of any AE (including SAEs) to the use of the study drug, as related or not related, based on clinical judgement and using all available information, and may include consideration of the following factors:
 - Possible alternative causes of the AE, including the disease under treatment, pre-existing conditions, concomitant use of other drugs, and presence of environmental or genetic factors.
 - The temporal association between study drug exposure and onset of the AE.
 - Whether the manifestations of the AE are consistent with known actions or toxicity of the study drug.
 - The AE resolved or improved with decreasing the dose or stopping use of the study drug (dechallenge). Judgement should be used if multiple products are discontinued at the same time.
- The causal relationship between the study drug and the AE will be assessed using one of the following categories:
 - Not Related: Factors consistent with an assessment of Not Related include:
 - Temporal relationship is lacking (eg, the event did not occur within a reasonable time frame following administration of the study drug); or
 - Other causative factors more likely explain the event (eg, a pre-existing condition, other concomitant treatments).
 - Related: Factors consistent with an assessment of Related include:
 - There is a positive temporal relationship (eg, the event occurred within a reasonable time frame following administration of study drug); or
 - The AE is more likely explained by the investigational product than by another cause (ie, the AE shows a pattern consistent with previous knowledge of the investigational product or the class of the study drug).

Follow-up of AEs and SAEs

- The Investigator is obligated to perform or arrange for the conduct of supplemental measurements and/or evaluations as medically indicated or as requested by the Sponsor or Medical Monitor to elucidate the nature and/or causality of the AE or SAE as fully as possible. This may include additional laboratory tests or investigations, histopathological examinations, or consultation with other health care professionals.
- New or updated information will be recorded in the originally completed CRF.
- The Investigator will submit any updated SAE data within 24 hours of receipt of the information.

Reporting of SAEs

SAE Reporting

- Email transmission of the SAE form is the preferred method to transmit this information.
- Initial notification via telephone does not replace the need for the Investigator to complete and sign the SAE form within the designated reporting time frames.
- Contact Information for SAE reporting: [contact]

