^c Including CBC, clinical chemistry, coagulation factors, viral serology screen, exploratory urine biomarkers, urinalysis and urine albumin. Coagulation factors and viral serology screen collected at Screening only.

^d Triplicate measurement will be taken at Screening only; for all other timepoints, single measurement is acceptable.

^e Screening, Day 0 and Day 21: completed anytime; Day 1, pre-dose (if not done on Day 0) and 6 (±2) hours post-dose; Day 7 and Day 14, 6 (±2) hours post-dose.

Visit Days	Day -28 to Day -1 (Screening)	Day 0* (Baseline)	Day 1	Day 7 (±1)	Day 14 (±1)	Day 21 (±1) End of Clinical Trial or Early Termination
------------	-------------------------------	-------------------	-------	------------	-------------	--

^fThe TETRAS Performance assessment will be captured on video for central reading. The local rater will rate the same TETRAS Performance assessment that is captured on video. The Screening video will be independently assessed for eligibility.

^gTo be performed 2 consecutive times separated by at least 30 minutes, the first of the two accelerometer assessments should be completed immediately after the TETRAS Performance assessment. All 3 maneuvers in the upper limb item (sub-items 4a, 4b, and 4c) will be completed for both arms, first for the RIGHT arm and then for the LEFT.

^hDay 1: 0 (pre-dose); Day 1, 7 and 14; post-dose immediately after completion of the 2nd accelerometer-based upper limb assessment; When PK sampling timepoints coincide with the TETRAS Performance timepoints or accelerometer-based assessment timepoints the PK sample is to be obtained last.

ⁱOptional samples collected at sites that have capabilities to perform serial sample collection: Day 1, 7 and 14: 0 (pre-dose), 0.5, 1, 2, 3, 4, 6, 8, 10, 12, 24 hours post-dose. All collection times up to 4 hours post-dose have a ±15 min window and a ±30 min window thereafter. 24-hour timepoint samples are to be taken prior to the AM dose. When PK sampling timepoints coincide with the TETRAS Performance timepoints or accelerometer-based assessment timepoints the PK sample is to be obtained last.

^jAdministered in clinic on Day 1. All other days it should be taken in the morning, within 30 minutes after breakfast. On Day 1 participant should be observed in clinic for approximately 6 hours before discharge. Study drug is dispensed (20 mg QAM for Day 1 to Day 7; 40 mg QAM for Day 8 to Day 14).

Table 3: Schedule of Activities (SoA) – Part B

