^b Vital signs include pulse rate, respiratory rate, temperature, and blood pressure. Blood pressure must be measured once after the participant has been supine for at least 5 minutes and once after the participant has been standing for at least 2 minutes. On Day 1, vital signs should be measured pre-dose, 2 hours post-dose (±30 min), and 6 hours post-dose (±30 min).

^c Including CBC, clinical chemistry, coagulation factors, viral serology screen, urinalysis, and urine albumin. Coagulation factors and viral serology screen collected at Screening only.

^d A triplicate measurement must be taken at Screening only; for all other timepoints, a single measurement is acceptable.

^e TETRAS can be completed anytime at Screening and Day 70. On other days, the following timing should be followed:

Day 1: pre-dose and 6 (±2) hours after a 20 mg QAM dose

Day 7: 6 (±2) hours after a 40 mg QAM dose

Day 21: 6 (±2) hours after an 80 mg (or highest tolerated dose) QAM dose

Day 42: pre-dose and 6 (±2) hours after a 120 mg (or highest tolerated dose) QAM dose

Day 56: 6 (±2) hours post-dose

^f The TETRAS Performance assessment will be captured on video for central reading. The local rater must rate the same TETRAS Performance assessment as that which is captured on video for central reading. The Screening video will also be independently assessed for eligibility.

^g Kinesia ONE assessments must be completed immediately after the TETRAS Performance assessments (including both pre-dose and post-dose assessments on Day 1 and Day 42). After each TETRAS Performance assessment, Kinesia ONE assessments should be completed twice separated by at least 30 minutes. All 3 maneuvers in the upper limb item (sub-items 4a, 4b, and 4c) will be completed for both arms, first for the RIGHT arm and then for the LEFT.

^h For visits with multiple TETRAS assessments, the TETRAS ADL subscale should only be assessed once. On Day 1, the ADL subscale should be completed pre-dose. On day 42, the ADL subscale should be completed 6 (±2) hours after the QAM dose.

ⁱ On Day 1 and Day 42 blood samples should be collected at the following timepoints: pre-dose and 0.5, 1, 2, 4, and 6 hours post-dose. The 6-hour post-dose sample will be collected immediately after completion of the second Kinesia ONE assessment. When PK sampling timepoints coincide with the TETRAS

Study Phase	Screening		Open-label Titration								Double-Blind Randomized Withdrawal	Safety Follow-up	

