8.2.4.1. Monitoring for Safety Laboratory Assessments of Special Interest

Renal function monitoring will be based on the Kidney Disease Improving Global Outcomes (KDIGO) guidelines and criteria for acute kidney injury (AKI)(Kellum 2012). According to the KDIGO guidelines, AKI is defined as any of the following:

- Increase in SCr by ≥ 0.3 mg/dL (≥ 26.5 $\mu\text{mol/L}$) within 48 hours; or
- Increase in SCr to ≥ 1.5 times baseline, which is known or presumed to have occurred within the prior 7 days

If a participant's laboratory values exceed these thresholds, dosing of that participant will be stopped and the laboratory tests will be repeated. Pending the results of these tests, a discussion will occur to determine pausing, stopping or continuing dosing the specific participant and/or the remainder of the participants in the study. Throughout the duration of the clinical trial,

participants should immediately notify the study team if there are any significant changes in their urine frequency or volume.

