5.8.2 Laboratory Test Results

Descriptive statistics for all reported and change from baseline values will be summarized by test category, laboratory test, and visit. Only the original assessment for each visit day will contribute to descriptive statistics; repeat or unscheduled assessments will not be included in the calculation of descriptive statistics by visit. All laboratory test results data (including pregnancy test and urine drug screen data and any repeat or unscheduled assessments) will be listed by study part, participant, and visit.

Descriptive statistics for all reported and change from baseline values for KIM-1, urine creatinine, and KIM-1 per urine creatinine ratio will be summarized by test and visit. Results will be listed by study part, participant, and visit.

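### Part B measures urine albumin without urine creatinine, so above 40 mg albumin can be corrected for dilution only roughly, and the SAP plans no correction in either part

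*Protocol*

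**What the plan says.** Protocol Appendix Table 1 lists urinary albumin among the other tests with no restriction by part. The entry beneath it reads "Urinary creatinine (Part A only". SAP Appendix 3, Table 3, carries the same two entries.

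The schedules agree. Footnote c to Table 2 (Part A) covers "exploratory urine biomarkers, urinalysis and urine albumin". Footnote c to Table 3 (Part B) reads "Including CBC, clinical chemistry, coagulation factors, viral serology screen, urinalysis, and urine albumin", with no urine creatinine and no urine biomarkers. The urinalysis panel applies to both parts and includes "Specific gravity".

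SAP Section 5.8.2 gives reported values and changes from baseline for every laboratory test by visit. It then adds a separate line: "KIM-1, urine creatinine, and KIM-1 per urine creatinine ratio will be summarized by test and visit". It names no albumin-to-creatinine ratio and no other adjustment of albumin.

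On renal safety, Protocol Section 8.2.4.1 states "Renal function monitoring will be based on the Kidney Disease Improving Global Outcomes (KDIGO) guidelines and criteria for acute kidney injury". Its thresholds are set on serum creatinine, for example "Increase in SCr by ≥ 0.3 mg/dL" within 48 hours.

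**The concern.** The concentration of albumin in a urine sample depends on how much albumin is excreted and on how dilute the urine is. Dividing by creatinine from the same sample largely removes the second influence. The SAP does this for KIM-1 but not for albumin.

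Changes in clinical laboratory results are a primary endpoint of Part B, and only Part B takes participants above 40 mg. Hydration is also unlikely to be constant across its laboratory visits. Baseline laboratory tests may be done on Day -1. On Day 42 dosing is in the clinic, with only water and permitted medications before breakfast. The doses on Days 7 and 21 are taken at home. A change from baseline in unadjusted albumin may therefore reflect hydration, and a real rise may be masked in dilute urine.

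**Working it through.** **Step 1. What is collected, and where.**

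| Item | Part A | Part B | Source |
|---|---|---|---|
| Urine albumin | yes | yes | Protocol Tables 2 and 3, footnote c; Appendix Table 1 |
| Urine creatinine | yes | not required | Appendix Table 1; SAP Table 3 |
| Specific gravity | yes | yes | Appendix Table 1, urinalysis |
| Exploratory urine biomarkers | yes | not listed | Footnote c of each table |
| Serum creatinine | yes | yes | Appendix Table 1, chemistry |
| Highest planned dose | 40 mg | 120 mg | Protocol Sections 6.1.1 and 6.1.2 |
| Dilution correction of albumin in the SAP | none | none | SAP 5.8.2 |

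A blacked-out entry follows urinary creatinine in Appendix Table 1. It is not counted as missing.

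**Step 2. Doses at the Part B laboratory visits.** Table 3 places open-label laboratory tests on Days 7, 21 and 42, where the titration schedule plans 40, 80 and 120 mg. The planned open-label visits above 40 mg are therefore those at 80 and 120 mg. Doses of 60 and 100 mg are sampled only in participants held there.

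**Step 3. Size.** The documents give no figure for urine albumin, urine creatinine or their variability, so there is nothing to reproduce. Everything below is illustration on assumed values.

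*Constant excretion, varying volume.* Assume 20 mg/day albumin, 1.2 g/day creatinine and urine volume V of 0.75 to 3.0 L/day.
- Unadjusted albumin = 20/V: 20/0.75 = 26.7 mg/L and 20/3.0 = 6.7 mg/L, a 4.0-fold swing with no change in excretion.
- Albumin-to-creatinine ratio = (20/V)/(1.2/V) = 16.7 mg/g at every volume.
- Specific-gravity adjustment = albumin × 0.015/(SG − 1), assuming SG − 1 is inversely proportional to V and equals 0.015 at 1.5 L. Over volumes of 0.75, 1.0, 1.5, 2.0 and 3.0 L, adjusted albumin runs from 12.5 to 13.6 mg/L if SG is read to 0.001 (13.6/12.5 = about 1.1-fold). It runs from 10.0 to 15.0 mg/L if SG is read to 0.005 (1.5-fold). Only rounding error enters here, so these are favourable figures for specific gravity.

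*Change from baseline.* Let s be the within-person SD of log urine concentration, with independent visits and no renal change. The log change has SD √2·s.
- 95% range for one person: a factor of exp(1.96·√2·s) in either direction.
- 95% CI half-width for the geometric mean change at n = 12: a factor of exp(2.201·√2·s/√12), where 2.201 is the t quantile on 11 degrees of freedom.

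| s (assumed) | Individual change, factor | Mean change at n = 12, CI factor |
|---|---|---|
| 0.3 | 2.3 | 1.3 |
| 0.5 | 4.0 | 1.6 |
| 0.7 | 7.0 | 1.9 |

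The SAP reports arithmetic means, SDs and medians, so the last column shows scale and is not a forecast of a planned output.

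**The case against.** The case for leaving the plan alone has four parts.

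1. *Renal monitoring does not rest on albumin.* The acute kidney injury criteria use serum creatinine, which is in the chemistry panel for both parts. Urinalysis also gives protein and blood, with microscopy when triggered. Participants must report marked changes in urine frequency or volume, and further tests are allowed at any time. This stands. A reader might infer that renal safety monitoring fails in Part B, or that renal interest attaches specifically to 60 to 120 mg. The documents support neither: Section 8.2.4.1 applies throughout the trial at every dose, and no visible threshold uses urine albumin.

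2. *Dilution can be corrected.* Specific gravity is measured in both parts. This also stands, and it rules out the tempting claim that albumin and dilution cannot be separated at all. But the correction is rougher than a creatinine ratio, and the SAP does not plan it.

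3. *The sample type and the size are not documented.* Neither document says whether urine is a spot or a timed collection, and handling is left to the Laboratory Manual. No timed collection is described either, so a single sample is the natural reading, but it is an inference. The figures above rest wholly on assumed variability.

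4. *Retained urine cannot be presumed.* The SAP describes some trial conduct in the past tense, and no text says that Part B urine is kept. This bears on which remedy is feasible, not on whether the gap exists.

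None of this makes unadjusted albumin interpretable, and none of it explains why Part A, which has both measurements, has no ratio.

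**Conclusion.** The point holds in a limited form. Part B requires urine albumin without urine creatinine, so no albumin-to-creatinine ratio can be formed above 40 mg. Only a rough adjustment by specific gravity is possible there, and the SAP specifies none for either part. What suffers is the interpretation of one descriptive safety variable within a Part B primary endpoint. No serum-creatinine criterion is affected, and no hypothesis test of safety is planned.

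The absence of the ratio is a matter of record. Its practical weight depends on how much urine concentration varies within a person. Over the assumed log-SDs, dilution alone could move an individual's albumin by a factor of 2.3 to 7, so individual changes smaller than that would be hard to read. The point merits an inexpensive improvement and does not invalidate the safety assessment.

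**What to change.** - Remove the Part A restriction on urinary creatinine in Protocol Appendix Table 1 and SAP Table 3, and add urine creatinine to footnote c of Table 3. Assay it on the Part B urine taken for albumin, at baseline as well as after dosing, so that a change in the ratio can be formed.
- In SAP Section 5.8.2, derive the albumin-to-creatinine ratio and summarize reported values and changes from baseline at each visit, in both parts. Part A needs no new data, provided its albumin and creatinine come from the same sample.
- If Part B urine is no longer available, summarize albumin adjusted by the specific gravity of the same urinalysis. State the formula and the resolution to which specific gravity is read, and note that unadjusted albumin is confounded by dilution.

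The cost is one inexpensive add-on assay and one extra derivation. The change to Appendix Table 1 also needs a protocol amendment with the ethics review described in Protocol Section 10.1. The Part A ratio and the specific-gravity fallback need only SAP text.
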